8.3.3 Analysis of Secondary Endpoints

1. PPVs on a per-patient and per-region-basis of ^{68}Ga -PSMA-11 PET for detection of tumor location confirmed by histopathology/biopsy, clinical and conventional imaging follow-up will be calculated and reported along with the corresponding two-sided 95% confidence intervals. The confidence intervals will be constructed using the Wilson score method. PPV will be reported for each of the three blinded readers independently.
2. Sensitivity and PPVs on a per-patient and per-region basis of ^{68}Ga -PSMA-11 PET for detection of tumor location confirmed by histopathology/biopsy will be summarized in tabular format. Ninety-five percent confidence intervals of sensitivity, specificity, NPV and PPV will be calculated using the Wilson score method. These will be reported for each of the three blinded readers.
3. Detection rates on a per-patient basis of ^{68}Ga -PSMA-11 PET stratified by PSA value (0.2 - <0.5, 0.5 - <1.0, 1.0 - <2.0, 2.0 - <5.0, ≥ 5.0) will be summarized in tabular format and compared between PSA strata using chi-square analysis. Detection rate will also be stratified by history of prostatectomy, radiation or both; as well as by whether the patient is on androgen deprivation therapy (ADT). We will use local interpretations for this analysis.
 - a. Detection rate is defined as number of patients with PSMA positive disease, independent of pathology, imaging or clinical follow-up. A detection rate will be reported for each reader independently stratified by PSA.
4. The impact of ^{68}Ga -PSMA-11 PET on clinical management in BCR patients will be evaluated using descriptive statistics.
5. Inter-reader reproducibility for positivity at the patient level and region level will be reported using the Fleiss' Kappa test for multiple readers. We will use the three blinded reads for this analysis.
6. Safety will be reported descriptively as rates of patient reported adverse events. Additionally, adverse events will be characterized and quantified by CTCAE 4.03.

9 Study Management

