3.3.1 Inclusion Criteria

1. Histopathologically proven prostate adenocarcinoma.
2. Rising PSA (at least two consecutive rising PSAs) after definitive therapy with prostatectomy or radiation therapy (external beam or brachytherapy).
 - a. Post radical prostatectomy (RP) – AUA recommendation for biochemical recurrence after radical prostatectomy
 - i. PSA greater than or equal to 0.2 ng/mL measured more than 6 weeks after RP.

- b. Post-radiation therapy –ASTRO-Phoenix consensus definition of biochemical recurrence after radiation therapy
 - i. Nadir + greater than or equal to 2 ng/mL rise in PSA
3. Karnofsky performance status of ≥ 50 (or ECOG/WHO equivalent).
4. Age > 18.
5. Ability to understand a written informed consent document, and the willingness to sign it.

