Of our first cohort of patients, 19% of patients underwent biopsy after a positive PSMA PET imaging. Based on biopsy results there was 100% sensitivity and 87% specificity. There were no True Negatives or False Negatives on biopsy. Imaging follow-up is not complete for our first study so we cannot estimate the percent of patients that will have imaging follow-up, but it appears that roughly 15 to 20% of patients will have imaging follow-up. Consistent with our second protocol, we anticipated that the sensitivity for the four regions and for all regions combined using conventional imaging ranges from 30-60%. An overall sensitivity for ^{68}Ga -PSMA-11 PET of at most 50% will be considered as unacceptably low. Hence, the null hypothesis that the sensitivity is at most 50% will be tested against the alternative hypothesis that the sensitivity is greater than 50%. It is hypothesized that ^{68}Ga -PSMA-11 PET imaging on the per-region and per-patient basis will substantially increase the sensitivity for the four regions to at least 70%. A sample size of 75 true positives is required for rejecting the null hypothesis that the sensitivity is at most 50% with 90% power at the one-sided 0.01 ($=0.05/5$ – a Bonferroni adjustment for evaluating the sensitivity for the four regions and for all regions combined) significance level, assuming an average regions specific prevalence of 20%. Although 19% of patients underwent biopsy and 15% of patients have imaging follow-up, we anticipate that the biopsy rate will fall in this study as referring clinicians become more comfortable with the imaging results. Therefore, we will combine imaging and biopsy follow-up in the primary aim, and will require 375 with both imaging and/or biopsy follow-up in order to power the analysis at a per region level. Assuming a prevalence rate of 20% for disease in each individual region, a total sample size of 1,500 patients is required. In summary, the proposed target accrual of 1,500 patients (375 with biopsies or imaging follow-up) will provide adequate power for detecting the anticipated improvement in the sensitivity for both the per-patient and per-region based ^{68}Ga -PSMA-11 PET imaging. However, a sample size of 107 patients with biopsies/follow-up in total is sufficient for detecting the anticipated improvement in sensitivity when evaluating per-patient based sensitivity.

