- (2) True negative patient: in the absence of True Positive or False Positive lesions, a patient will be considered a True Negative if there is pathology that is negative for disease and corresponding lesion is negative by PSMA PET.
 - (3) False positive patient:
 - (a) Pathology confirms a false positive lesion that is read as positive on PSMA PET.
 - (b) In the absence of pathology: there are no true positive regions, and there is a region that is categorized as false positive based on imaging or clinical follow-up.
 - (4) False negative patient: in the absence of True Positive or False Positive lesions, a patient will be considered a False Negative if there is pathology that is positive for disease and corresponding lesion is negative by PSMA PET. Additionally, patients without evidence of disease on PSMA PET but with biochemical evidence of disease will be considered a False Negative.
- ii) Region level evaluation: Each patient will have four evaluable regions (Table 1: prostate bed, pelvis, extrapelvic soft tissue, and bone metastases). Each region will be categorized as true positive or false positive as described above. Regions without evidence of PSMA positive disease or deemed inevaluable will not be included in the analysis.
 - (1) True positive region:
 - (a) Pathology confirms a PSMA avid lesion as a true positive in the region.
 - (b) In the absence of pathology, clinical or imaging follow-up demonstrates a true positive lesion within the region independent of the presence of an inevaluable lesion or a false positive lesion
 - ie true positive disease will supersede a false positive lesion in the region based analysis if based on imaging/clinical follow-up
 - (2) True negative region: in the absence of True Positive or False Positive lesions within a region, the region will be considered a True Negative if there is pathology that is negative for disease in the region and corresponding lesion is negative by PSMA PET.
 - (3) False positive region:
 - (a) Pathology confirms a PSMA avid lesion as a false positive in the region

- (b) In the absence of pathology, there are no true positive lesions in the region, and there is a false positive lesion by clinical or imaging follow-up.
- (4) False negative region: in the absence of True Positive or False Positive lesions in a region, the region will be considered a False Negative if there is pathology that is positive for disease in the region and corresponding lesion is negative by PSMA PET.

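### Specificity and NPV intervals are planned, but the classification rules supply few or no usable true negatives and contradict their own definitions

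*Combined protocol and SAP*

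**What the plan says.** Section 8.3.3 item 2 covers the analysis confirmed by histopathology or biopsy, per patient and per region, for each of the three blinded readers. It states: "Ninety-five percent confidence intervals of sensitivity, specificity, NPV and PPV will be calculated using the Wilson score method". The objectives in section 2 name sensitivity and PPV only.

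The cells of the 2x2 table come from 8.3.2 d):

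- **True negative patient.** If there are no true or false positive lesions, "a patient will be considered a True Negative if there is pathology that is negative for disease" and the corresponding site is negative on PET. A true negative region is defined in the same way.
- **False negative patient.** Besides those with positive pathology at a PET-negative site, "patients without evidence of disease on PSMA PET but with biochemical evidence of disease will be considered a False Negative".
- **Regions.** "Regions without evidence of PSMA positive disease or deemed inevaluable will not be included in the analysis". Definitions of true negative and false negative regions follow directly after this sentence.

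Inclusion criterion 2 requires of every participant: "Rising PSA (at least two consecutive rising PSAs) after definitive therapy".

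On the first protocol, section 8.2.1 reports: "Based on biopsy results there was 100% sensitivity and 87% specificity". The next sentence reads: "There were no True Negatives or False Negatives on biopsy". The biopsies were selected: "19% of patients underwent biopsy after a positive PSMA PET imaging".

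**The concern.** Specificity is TN/(TN+FP) and NPV is TN/(TN+FN), so both need a well-defined supply of true negatives. Here one rule turns PET-negative patients into false negatives and another drops PET-negative regions. The resulting figures would largely describe the classification and biopsy-selection rules, not the scan. Because the definitions conflict, two analysts could also obtain different values from the same data.

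The data are meant to be pooled for an NDA submission (1.1). The region exclusion reaches further than item 2, because region-level sensitivity is part of the primary objective and is one of the quantities for which 8.2.1 sets the sample size. The first-protocol figure shows how easily a measure is mislabelled when the true negative cell is empty.

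**Working it through.** **Inputs from the documents.** First protocol: TN = 0 and FN = 0 on biopsy, with 100% sensitivity and 87% specificity stated (8.2.1). TP and FP counts are not given. Expected PET-negative share: 24% (8.2.1). Patients with biopsy or imaging follow-up: 375 of 1,500 (8.2.1). No FP count is given for this trial, so the FP values below are assumptions.

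**Step 1: the plan's own figure.** With TN = FN = 0:

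- Sensitivity = TP/(TP+0) = 100%. This reproduces, and is automatic.
- Specificity = 0/(0+FP) = 0%, or undefined if FP = 0. The stated 87% does not reproduce. It would need 0.87/0.13 = 6.7 true negatives per false positive.
- NPV = 0/0.
- PPV = TP/(TP+FP). This is the only one of the four that can be 87%, for example 13/15 = 86.7% or 20/23 = 87.0% (illustrative counts).

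**Step 2: region level, exclusion sentence read literally.** A region must be PET-positive to be counted, so TN = 0 and FN = 0.

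- Specificity = 0/FP = 0%.
- NPV = 0/0: undefined, with no Wilson interval.
- Sensitivity = TP/(TP+0) = 100%. Against the 50% null at one-sided 0.01 in 8.2.1, the exact p-value for n out of n is 0.5^n. Seven true positive regions suffice to reject (0.5^7 = 0.0078), however many diseased regions the scan missed.

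**Step 3: patient level, biochemical false negative sentence governing.** Every participant has biochemical recurrence, so every fully PET-negative patient is a false negative. If no other true negative arises, TN = 0. For 0/n the Wilson upper limit is z²/(n+z²), with z² = 3.84.

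| Measure | Count | Estimate | Wilson 95% |
|---|---|---|---|
| Specificity | 0/10 (FP assumed) | 0% | 0 to 27.8% |
| Specificity | 0/20 (FP assumed) | 0% | 0 to 16.1% |
| NPV | 0/90 (24% of 375) | 0% | 0 to 4.1% |
| NPV | 0/360 (24% of 1,500) | 0% | 0 to 1.1% |

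**Step 4: patient level, true negative definition governing.** Suppose 5 of 90 PET-negative patients have negative pathology (assumed) and the other 85 stay false negatives. Specificity with 10 assumed FP is 5/15 = 33% (Wilson 15 to 58%). NPV is 5/90 = 5.6% (2.4 to 12.4%). The same scans thus give a specificity of 0% or 33%, depending only on which rule is applied.

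**Step 5: patient level, biochemical sentence not applied because item 2 is pathology-based.** Biopsy is aimed at PET-positive findings (8.3.2 c). If the first protocol's pattern of no true or false negatives recurs, specificity is 0/FP and NPV is 0/0.

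**The case against.** The strongest reply is that the plan does define true negatives, for patients and for regions, by negative pathology at a PET-negative site. That stands. A reader might infer that the rules leave no true negatives at all, so that both measures must be reported as 0%. The documents do not support this, for four reasons.

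- A PET-negative patient with negative pathology meets both the true negative definition and the biochemical false negative sentence. 8.3.2 d) ranks pathology above imaging and clinical follow-up, which arguably favours true negative, but it does not say whether this overrides the biochemical sentence.
- A patient whose PET-positive lesions are all inevaluable, with negative pathology at a PET-negative site, can be a true negative without meeting the biochemical sentence.
- Classification is done per blinded reader. A site biopsied after a positive local read may be negative for a central reader, and negative pathology there could give a true negative.
- At region level, NPV is undefined, not 0%.

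It can also be argued that the region exclusion was meant only for regions without pathology. That would rescue the region definitions, but the sentence carries no such limit. The allowance in 8.3.2 d) for case-by-case deviation does not resolve the conflict either.

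Finally, specificity and NPV are not objectives, and the success rule in 8.3.2 uses per-patient sensitivity. That limits the consequences but is also why deletion costs so little.

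**Conclusion.** The point holds as a conflict between rules, with few or no usable true negatives; it is not a proven empty cell. At region level, with the exclusion read as written, specificity is 0% whenever FP > 0, NPV is undefined, and sensitivity is 100% by construction. At patient level, specificity and NPV are 0% only if the biochemical false negative sentence governs, no other true negative arises, and FP and FN exceed zero. The interval widths rest on assumed FP counts and, for NPV, on the expected 24% PET-negative share.

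The 87% in 8.2.1 is a separate and secondary matter. It cannot be a specificity when there are no true negatives, and by elimination it fits only PPV. A reader might infer that the trial is bound to repeat this mislabelling. The documents do not show that: the first protocol has a mislabelled or miscounted statistic, whereas the plan has conflicting rules. The sample size is built on 50% against 70% sensitivity and does not use the 87%.

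The plan should be corrected before the analysis. The region-level sensitivity consequence carries the most weight, because it touches the primary objective.

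**What to change.** 1. In 8.3.3 item 2, delete specificity and NPV. Alternatively, restrict them to sites sampled by pathology, say so in the table titles, and state that a zero denominator is reported as not estimable.
2. In 8.3.2 d) i), state which rule takes precedence when a fully PET-negative patient has negative pathology, and whether the biochemical false negative sentence applies in the histopathology-only analysis.
3. In 8.3.2 d) ii), reconcile the exclusion sentence with the true and false negative region definitions, so that PET-negative regions with positive pathology count in the denominator of region-level sensitivity.
4. In 8.2.1, check the 87% against the first protocol's TP and FP counts and correct the label.

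The cost is wording in an amendment. No data collection changes, and no objective is lost by deleting the two measures. Item 3 can lower region-level sensitivity below 100%, as a real estimate must be able to do. Few PET-negative regions may have pathology, so the number contributing to the denominator should be reported.

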3.2 Number of Subjects

It is anticipated that 1,500 patients will be enrolled in this study.

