6.1.1.1 Screening Assessments

The Screening procedures and assessments must be completed within 30 days of the day 1 Visit.

- Laboratory values: all patients must have a recent PSA (within 30 days prior to study enrollment) consistent with BCR
 - If only one PSA greater than or equal to 0.2 ng/dL post radical prostatectomy is available, then a second confirmatory PSA must be checked prior to the ⁶⁸Ga-PSMA-11 PET study.
- Pathology: all patients must have histopathology/biopsy of the prostate with a documented Gleason score
- Performance status: all patients must have their Karnofsky performance status (or ECOG/WHO equivalent) evaluated (Appendix 1).
- Change in management: A pre-imaging survey of planned clinical management will be performed prior to ⁶⁸Ga PSMA-11 PET/CT imaging.

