8.2.2 Accrual estimates

We estimate that roughly 250 patients with prostate cancer will be enrolled in this trial per year. Over a two-year period this will result in up to 500 patients being enrolled in the study.

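### Radiation-only patients can fall only in the two PSA strata at or above 2.0 ng/mL, so the pooled comparison of detection between PSA strata mixes PSA with prior therapy across that boundary

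*Combined protocol and SAP*

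**What the plan says.** Section 3.3.1 has two routes into the trial. After prostatectomy the criterion is "PSA greater than or equal to 0.2 ng/mL measured more than 6 weeks after RP". After radiation it is "Nadir + greater than or equal to 2 ng/mL rise in PSA". Section 6.1.1.1 ties the threshold to the PSA at entry: "all patients must have a recent PSA (within 30 days prior to study enrollment) consistent with BCR".

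Section 8.3.3, item 3, reports per-patient detection "stratified by PSA value (0.2 - <0.5, 0.5 - <1.0, 1.0 - <2.0, 2.0 - <5.0", with a fifth stratum at 5.0 and above. The rates are then "compared between PSA strata using chi-square analysis". The next sentence reads "Detection rate will also be stratified by history of prostatectomy, radiation or both", and adds androgen deprivation therapy as another factor. The item does not say that prior therapy is crossed with PSA, that the test is restricted to one therapy group, or that it is adjusted. It gives no significance level or power for this test.

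**The concern.** The entry rule links PSA to treatment history by construction. Three of the five strata hold only patients with a prostatectomy; the upper two hold those patients plus every radiation-only patient. A comparison of strata below 2.0 with strata above it therefore compares PSA levels and case mix together. A PSA table and a separate prior-therapy table cannot disentangle the two when one therapy group is absent from three strata.

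Detection by PSA is a listed secondary objective (section 2.2), and section 1.1 says the data are meant to be pooled for a marketing application. A reader will take the table as the detection to expect at a given PSA. At 2.0 and above, the pooled rate depends on how many radiation-only patients happened to enrol, and it may describe neither group.

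**Working it through.** **Step 1: where radiation-only patients can fall.** Entry PSA ≥ nadir + 2, and nadir ≥ 0, so entry PSA ≥ 2.0 ng/mL. The stratum cut-points include exactly 2.0. The strata 0.2 to <0.5, 0.5 to <1.0 and 1.0 to <2.0 therefore contain no eligible radiation-only patient. This follows from the documents alone. Section 3.3.1 does not say which threshold applies to a patient with both treatments, so the statement is limited to radiation-only patients.

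**Step 2: effect on the pooled test.** The plan gives no figure to reproduce. Inputs from the documents: five strata (4 degrees of freedom); 1,500 patients (section 3.2, "It is anticipated that 1,500 patients will be enrolled in this study"); 500 as a lower case (section 8.2.2, "Over a two-year period this will result in up to 500 patients being enrolled in the study"). Assumptions, because the documents are silent: alpha 0.05; 25% radiation-only; patients with prostatectomy spread evenly over five strata; radiation-only patients split evenly over the top two; detection 70% after prostatectomy and 70% + d radiation-only; no PSA effect within either group.

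With 1,500 patients, each lower stratum holds 1,125/5 = 225. Each upper stratum holds 225 + 375/2 = 412.5, of whom 187.5/412.5 = 45.5% are radiation-only. The expected rate is 70% in the lower strata and 70% + 0.455d in the upper two. The noncentrality is λ = Σ nᵢ(pᵢ − p̄)² / [p̄(1 − p̄)], and the rejection probability is P(χ²₄(λ) > 9.488).

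For d = 10 points: the upper rates are 74.5%, p̄ = 72.5%, and λ = (675 × 0.0250² + 825 × 0.0205²)/(0.725 × 0.275) = 3.85, so the probability is 31%.

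| Therapy difference d | Rates, lower three / upper two | λ (1,500) | Rejects, 1,500 | Rejects, 500 |
|---|---|---|---|---|
| 0 | 70% / 70% | 0 | 5% | 5% |
| 5 points | 70% / 72.3% | 0.94 | 10% | 7% |
| 10 points | 70% / 74.5% | 3.85 | 31% | 12% |
| 20 points | 70% / 79.1% | 16.36 | 92% | 43% |

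Other shares with 1,500 patients: 10% radiation-only and 10 points gives 10%; 40% and 20 points gives 99.8%.

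**Step 3: the same comparison within therapy groups.** Tests restricted to patients with prostatectomy (five strata, 4 df), or summed with the radiation-only test (two strata, 5 df in total), were simulated with 20,000 trials per scenario. The scenarios covered radiation-only shares of 10% to 40%, differences of 0 to 20 points, and both sample sizes. They rejected 4.7% to 5.3% of the time throughout.

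**Step 4: with the gradient the protocol reports.** Section 1.2 cites detection of 50% below 1 ng/mL and above 85% above 2 ng/mL, not split by prior therapy. Take 50/50/70/85/85% across the strata (the 70% is an assumption) and 85% in radiation-only patients. The pooled test and the prostatectomy-only test then each reject at least 99.9% of the time, for 500 or 1,500 patients and shares of 10% to 40%. If radiation-only detection is instead 10 points higher or lower at the same PSA (25% share), the pooled rate in the upper strata becomes 85% ± 0.455 × 10 points, that is 89.5% or 80.5%. The prostatectomy rate stays at 85%.

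**The case against.** A reader might infer that the planned test will show a PSA effect where none exists. The documents do not support that.

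- The plan describes detection rates by PSA in the enrolled population and claims no PSA effect independent of prior therapy. In the scenarios of step 2 the stratum rates really do differ, so the chi-square is not in error for its own marginal null hypothesis.
- No section gives the radiation-only share or detection by prior therapy. The 92% figure needs a 20-point difference; with none, the test holds its 5%.
- Section 1.2 points to a real and strong gradient, under which the pooled and restricted tests reach the same decision.

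All three points stand, and they limit the issue to the size and attribution of the gradient.

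It can also be said that the prior-therapy sentence follows the PSA sentence directly and may have been meant as a cross-classification. That reading is open, but the text does not state it, and even a crossed table would leave the test pooled. Finally, this is one secondary, largely tabular analysis with no success criterion. That is correct and sets the priority.

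**Conclusion.** The structural point is certain: by the entry rule, radiation-only patients are confined to the top two PSA strata, and the planned comparison does not account for this. Its consequence is conditional on detection differing by prior therapy at equal PSA. If radiation-only detection is higher, the gradient across 2.0 is exaggerated; if lower, it is flattened or masked. Comparisons among the three lower strata are untouched by radiation-only patients.

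The rejection rates of 5% to 92% illustrate sensitivity to assumed inputs; they are not a forecast for this trial. The more likely practical effect is a shift in the rates reported at PSA 2.0 and above, about 4.5 points per 10-point therapy difference at a 25% radiation-only share. This is a worthwhile low-cost improvement, not a threat to the trial's conclusions. The primary sensitivity analysis is unaffected.

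**What to change.** Keep the planned marginal table by PSA stratum. Add one table of detection by PSA stratum and prior therapy (prostatectomy only, radiation only, both), showing the three empty radiation-only cells as empty by design. Make the between-strata comparison in one of two ways, chosen in advance:

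- within prior-therapy groups: five strata in patients with a prior prostatectomy, and the top two strata in radiation-only patients; or
- as a Cochran-Mantel-Haenszel test stratified by the three prior-therapy categories. This also avoids pooling prostatectomy-only patients with those who had both treatments, whose detection may differ too.

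State the significance level, and state which PSA threshold applies to patients with both treatments, so that their possible strata are clear.

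The cost is a few lines of wording and one more table, from variables the plan already uses. The downside is smaller cells in the radiation-only group, so estimates there will be less precise.

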8.1.2 Blinding

- For primary endpoint analysis of ⁶⁸Ga-PSMA-11 PET imaging studies central readers will be fully blinded to clinical information and any conventional imaging results. Central readers will have access to the concomitant CT or MRI used for attenuation purposes.
- For local interpretation of ⁶⁸Ga-PSMA-11 PET imaging studies, local readers will be unblinded to both clinical information and other conventional imaging data.
- For local interpretation of conventional imaging follow-up images 3-12 months post ⁶⁸Ga-PSMA-11 PET scan, local readers will be unblinded to all results and will be specifically informed of the location of ⁶⁸Ga-PSMA-11 PET positive lesions so that follow-up measurements may be performed on these lesions.

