8.3.2 Analysis of Primary Endpoints

Sensitivity on a per-patient and per-region-basis of ^{68}Ga -PSMA-11 PET for detection of tumor location confirmed by histopathology/biopsy, clinical and conventional imaging follow-up will be calculated and reported along with the corresponding two-sided 95% confidence intervals. The confidence intervals will be constructed using the Wilson score method. For successful completion of the primary endpoint, two of the three readers will need to have an 70% sensitivity for the detection of disease on a per patient level for the cases that have a) imaging follow-up, b) pathology correlation or c) combination of pathology and imaging follow-up and/or pathology correlation.

^{68}Ga -PSMA-11 PET Results Definition

a) Imaging interpretation ^{68}Ga -PSMA-11 PET:

Local Interpretations: PET images will initially be interpreted by a board certified nuclear medicine physician or a board-certified radiologist experienced in reading PET at the time of the imaging study at the institution that the study is being performed. These interpretations will not be used for final evaluation, and will not be reported as part of the primary or secondary endpoints.

Central Read Logistics: Imaging data will be anonymized and collected at a central site. PET data will be interpreted by three different readers in a random order at separate reading sessions. Cross sectional imaging (CT or MRI) from the ^{68}Ga -PSMA-11 PET will be available for anatomic correlate. The Central readers will be blinded to all other imaging results and all other clinical data.

Reader Positivity and Negativity Definition: Regions defined in Table 1 will be graded for the presence of suspected disease on a two-point scale by each reader (0=Negative or 1=Positive). A region will be judged as positive if at least one lesion in this region is visually positive.

Reader Training: ^{68}Ga -PSMA-11 PET/CT reading training set and guides will be provided and completion of this training will be required for all central review readers. Common pitfalls will be reviewed as part of the reader training.

Criteria for visual interpretation:

Regions of suspected disease will be graded on a two-point scale by each blinded reader (0=Negative or 1= Positive). A region will be judged as positive if at least one lesion in this region is visually positive.

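### Section 8.3.3 item 3 bases the detection-rate endpoint on local PET reads, but section 8.3.2 bars local reads from every secondary endpoint; the read source must be reconciled before analysis.

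*Combined protocol and SAP*

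**What the plan says.** Section 2.2 lists per-patient detection rate as a secondary objective, stratified by five PSA bands, by prior prostatectomy, radiation or both, and by ADT status. Section 8.3.3 item 3 plans tables for these strata and a chi-square comparison between the PSA bands, and names the read source: "We will use local interpretations for this analysis".

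Section 8.3.2, under Local Interpretations, describes a read at the imaging site: "PET images will initially be interpreted by a board certified nuclear medicine physician or a board-certified radiologist experienced in reading PET". It then limits its use: "These interpretations will not be used for final evaluation, and will not be reported as part of the primary or secondary endpoints". Under Central Read Logistics, the same section says: "PET data will be interpreted by three different readers in a random order at separate reading sessions".

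Item 3a defines the endpoint: "Detection rate is defined as number of patients with PSMA positive disease, independent of pathology, imaging or clinical follow-up". It continues: "A detection rate will be reported for each reader independently stratified by PSA". On blinding, section 8.1.2 says that for PET interpretation "local readers will be unblinded to both clinical information and other conventional imaging data".

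**The concern.** A secondary endpoint has been assigned a read source that another section excludes from all secondary endpoints. Two statisticians could build the tables and run the chi-square on different reads, one local and one central, and each could cite the protocol. If the text is not settled beforehand, the choice could be made after both sets of results are known.

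The two sources are not interchangeable. The clinical information open to local readers can include PSA, prior therapy and ADT status, which are the variables that define the strata. A reader who knows the PSA could read more or less readily in some strata than in others. Because detection rate is counted without regard to pathology or follow-up, no reference standard would reveal such a shift.

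**Working it through.** The documents give no figure that depends on this point, so the check is a comparison of the texts.

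1. **Is detection rate a secondary endpoint?** Yes. It is in section 2.2 and in the Abstract, and it is item 3 of the section headed Analysis of Secondary Endpoints.

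2. **Do item 3 and section 8.3.2 conflict?** Yes. Item 3 uses local reads. Section 8.3.2 names secondary endpoints in its exclusion and gives no exception. Obeying one sentence breaks the other.

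3. **Does another section resolve it?** No. Section 8.1.2 ties full blinding of the central readers to the primary endpoint analysis, so it neither requires nor forbids blinded reads here. Central Read Logistics describes three blinded reads without limiting them to a subset of patients or endpoints. No order of precedence between sections is stated.

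4. **Who is the reader in item 3a?** The local read is described as one physician's read at the site, and no fixed set of local readers is defined. Three central readers are defined. Item 1 uses almost the same construction for them: "PPV will be reported for each of the three blinded readers independently". Items 2 and 5 also name the three blinded readers. The natural reading is therefore the blinded readers, but item 3a does not use that word.

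5. **Do items 3 and 3a conflict with each other?** Not necessarily. Item 3a promises per-reader rates by PSA only, while item 3 also covers prior therapy and ADT. Local reads for the item 3 tables and chi-square, with blinded per-reader rates by PSA alongside, would satisfy both. The conflict with section 8.3.2 would remain.

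6. **Is the denominator given?** No. Item 3a defines the rate as a number of patients. Imaged patients in the stratum is the obvious intention, so this is a missing detail rather than an error.

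7. **Can the effect of the read source be computed?** No. The documents give no detection rates by type of read.

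**The case against.** The strongest reply is that the specific sentence governs. Item 3 names its read source deliberately, just as item 5 names the blinded reads for reproducibility, so the authors appear to choose reads analysis by analysis. This has force. It means that blinded reads cannot be imposed as the only correct reading. It does not remove the contradiction: if item 3 prevails, section 8.3.2 is wrong as written and needs an exception.

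A second reply is that little hangs on the test. Detection rate has no success criterion, alpha or power, and strong PSA gradients may survive a reader shift. Section 1.2 cites detection of 50% below 1 ng/ml and above 85% above 2 ng/ml. Take 85%, and assume 100 patients per group. The pooled proportion is (0.50 + 0.85)/2 = 0.675, and chi-square = 0.35² / (0.675 × 0.325 × 2/100) = 0.1225/0.0043875 = 27.9 on 1 df. If an assumed shift narrowed the rates to 55% and 80%, the pooled proportion is unchanged and chi-square = 0.25²/0.0043875 = 14.2, p about 0.0002. So the test could well reach the same conclusion on either source. The reported rates, which are the substance of this endpoint, could still differ.

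A reader might infer three stronger points, none of which the documents support:

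- **That unblinded local reads bias the detection rates.** The documents show a route by which this could happen but no evidence that it does, and no direction.
- **That items 3 and 3a flatly contradict each other.** Step 5 of the working gives a reading that satisfies both.
- **That section 8.3.1, by giving secondary endpoints to the patients who remain after those with histopathology, removes biopsied patients from the denominator.** That reading would also empty the histopathology-based secondary endpoint in item 2, so it is unlikely to be meant.

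**Conclusion.** The contradiction between section 8.3.2 and section 8.3.3 item 3 stands on the current text, and confidence in it is high. That confidence does not extend to which read source should win, because the documents do not settle it. That item 3a means the blinded readers is a strong inference, not a stated rule.

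The effect on the reported rates cannot be estimated from the documents. The concern about unblinding assumes that the clinical information available locally includes PSA, prior therapy or ADT status, which is plausible but not itemised. The reach is limited to one secondary endpoint. The primary sensitivity analysis, which uses the blinded central reads, and the sample size are untouched. The point should be corrected, but it does not threaten the trial's main conclusion.

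**What to change.** Before any analysis, the sponsor should adopt one of two options:

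- **(a) Blinded reads.** Change item 3 to the three blinded central reads and state which call feeds the single chi-square between PSA strata, for example the majority of the three. Without such a rule there would be three chi-squares and no way to handle disagreement. Show local reads as a supportive table, and amend section 8.3.2 to allow that table.
- **(b) Local reads.** Keep local reads for the item 3 tables and chi-square, and write that exception into section 8.3.2.

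Under either option, item 3a should:

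- say that each reader means each of the three blinded readers, and report their PSA-stratified rates alongside the main table;
- give the denominator as imaged patients with a read in that stratum, with the number read shown out of the number imaged.

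The planned chi-square stays. The cost is wording in sections 8.3.2 and 8.3.3 and one extra table, provided that all scans are read centrally, as section 8.3.2 implies by stating no subset. If central reading was meant only for the 375 patients with biopsy or imaging follow-up (an assumption), reading everyone would mean 3 × 1,500 = 4,500 reads instead of 3 × 375 = 1,125. The fix does not require that: the read and imaged counts would show the subset openly, and option (b) would keep all imaged patients with a local read in the main table.
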